4.0	06.05.2016	
 - Change in information about regulatory status of PICSO technology from CE-marked to non non-CE mark - Extension of recruitment beyond the period specified in the IRAS application form 	V3.0 20.06.2016
5.0	26.02.2018	
 - Extension of recruitment beyond the period specified in the IRAS application form - Extension of inclusion criteria to allow enrolment of all patients with ST elevation myocardial infarction, irrespectively of the coronary location of the culprit lesion 	V4.0 06.05.2016

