The Prepare-PICSO study represents the first-in-man experience with the PICSO device [21]. On a small sample of 15 patients with stable angina the PICSO treatment showed to be firstly safe and, as observed in the animal models, was associated to a significantly increase in coronary sinus pressure as well in mean CW pressure in the distal left anterior descending (LAD) coronary artery [21].

These findings have triggered the Prepare-RAMSES study in which PICSO treatment was investigated for the first time in man in patients with STEMI [22]. The results of the study have been recently published. The study was initially designed to include 30 patients with anterior STEMI with PICSO treatment for 90 minutes after the completion of primary percutaneous coronary intervention (PPCI). The study enrolled only anterior STEMI since expected to be responsive to the PICSO device, being mainly the anterior wall of the myocardium drained by the coronary sinus. The device resulted to be safe, with a median implantation time of 12 minutes. The primary endpoint was the reduction in IS at cardiac magnetic resonance (CMR) at 2-4 days and 4 months. The PICSO group was compared with a matched control group of patients.

Although the study did not show an overall difference in the reduction in IS in the PICSO group [22], IS reduction appeared to be significantly related to the quantity of PICSO treatment (pressure achieved in the coronary sinus x time of treatment) and significantly higher in the small subgroup of patients receiving high PICSO quantity.

It is possible that the study did not reach the primary endpoint due to some limitations in its design. First of all the small sample size has to be acknowledged, since the investigators managed to fully deliver the PICSO treatment only to 12 patients (63% of the initially intended sample size). Moreover, the study

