6. TRIAL DESIGN

The OxAMI-PICSO study is a prospective single centre observational cohort study of the use of PICSO in patients presenting for primary PCI for acute myocardial infarction. The OxAMI- PICSO study is based upon the established framework of the OxAMI study (Ethics Ref 11/SC/0397).

Patients, age 30-90, presenting with ST elevation myocardial infarction will be considered for inclusion in the study. Measurement of IMR before stenting is an essential prerequisite for the study: only patients with pre-stenting IMR > 40 will be considered eligible for the PICSO treatment. Patients with IMR≤ 40 will remain in the study but will not undergo PICSO treatment. The procedure for consent in patients undergoing emergency PCI will be as already established in the ongoing OxAMI study, and is discussed below in Section 8.1.2.

The PCI procedure will be undertaken in a standard fashion, and include the use of pressure wire measurements before and after stent deployment. Aspiration or distal protection devices may be used if clinically indicated and where vessel anatomy is suitable. The devices used and the procedural techniques will be driven by clinical decision making at the patient and institutional level, and carried out in accordance with the Oxford University Hospitals NHS Trust (OUHT) departmental guidelines for PCI.

PICSO treatment will be added on top of the conventional treatment.

The protocol will constitute of 5 main stages described in details in the next sections (Section 8.3).

Only patients with pre-stenting IMR > 40 and who assent to receive PICSO treatment will undergo 24 hours coronary angiogram with coronary physiology measurement, 24-48 hours CMR scan and 6 months CMR scan. Patients who assent to participate in the study but in whom the pre-stenting IMR ≤ 40, or those in whom the pre-stenting IMR > 40 but the participant declines PICSO treatment will remain in the study for blood sampling and clinical data collection at the same follow up time points (24 hours, 48 hours and 6 months). A summary of the study design, indicating the time points and procedures, is shown in Section 8.3.

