7.2. Inclusion Criteria

Participants must satisfy the following conditions:

- Male or Female, aged 30 to 90 years,
- Clinical presentation with STEMI
- Referred for coronary angiography with view to proceed to PCI with stenting.

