8.3.4 Stage 4: 24-48 hours post PCI

Full written consent to take part to the OxAMI-PICSO study is obtained as soon as practicable. The following study assessments may be carried out:

1. Repeat coronary angiogram for assessment of coronary physiology parameters assessment – for participants who receive the PICSO device only
2. Cardiac magnetic resonance - for participants who receive the PICSO device only
3. Venous blood sampling for biomarker measurement
4. Data Collection, Patient Reported Outcomes and Cardiovascular Outcomes

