12.2 Analysis of Endpoints

In keeping with our usual practice we will obtain expert statistical advice from the Centre for Statistics in Medicine (or equivalent) for each specific task. Summary statistics, including means, medians, and

variances, will be calculated at each time point and for each type of data (e.g. parameters derived from coronary physiology and CMR). The distribution of the levels will be described. It may be necessary to log transform the data before further statistical analysis. For each parameter an analysis of variance will be carried out at each time point.

Control group in OxAMI-PICSO study is represented by a highly matched group of patients underwent to primary PCI, with a prestenosing IMR > 40 and with available 24 hours recath and 24-48 hours/6 months CMR data. Matching will be performed by application of a propensity score matching analysis including the following predictors in the model: age, sex, pain to wire time, thrombotic burden (assessed as angiographic thrombus score), thrombus aspiration performance, stent volume, glycoprotein IIbIIIa inhibitors adoption.

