21. APPENDIX B: SCHEDULE OF PROCEDURES IN NON-PICSO GROUP

Procedures	NON-PICSO group						
	Pre-PCI	During PCI		6 hours	24 hours	48 hours	6 months
		Start of procedure	End of PCI				
Verbal assent	X						
Blood samples		X	X	X	X	X	X
Coronary physiology measurements (IMR, CFR, FFR)		X	X				
Informed written consent				X			
ECG	X		X	X			
Echocardiography					X		
Medical history Demographic data collection						X

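### The stated propensity-score list in 12.2 omits culprit vessel although any culprit location is now eligible, so the only infarct-size comparison is open to vessel imbalance, with an effect of unknown size and direction

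*Combined protocol and SAP*

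**What the plan says.** - **Matching.** Section 12.2 takes controls from OxAMI patients with pre-stenting IMR above 40 and available recath and CMR data. The propensity model includes seven predictors: "age, sex, pain to wire time, thrombotic burden (assessed as angiographic thrombus score), thrombus aspiration performance, stent volume, glycoprotein IIbIIIa inhibitors adoption".
- **Outcome analysis.** The same section states: "For each parameter an analysis of variance will be carried out at each time point". It names no covariate and no stratification.
- **Eligibility.** The version table in the Synopsis records that version 5.0 admits all STEMI patients "irrespectively of the coronary location of the culprit lesion". Section 7.2 agrees; its only infarct-related criterion is "Clinical presentation with STEMI".
- **Why location may matter.** Section 4.2 explains that the earlier STEMI study of the device took only anterior infarcts, "since expected to be responsive to the PICSO device, being mainly the anterior wall of the myocardium drained by the coronary sinus".
- **Who is imaged.** Under Section 6, only patients with IMR above 40 who assent to PICSO "will undergo 24 hours coronary angiogram with coronary physiology measurement, 24-48 hours CMR scan and 6 months CMR scan". Section 8.3.4 repeats this: "Cardiac magnetic resonance - for participants who receive the PICSO device only". Appendix B, headed "SCHEDULE OF PROCEDURES IN NON-PICSO GROUP", has no row for CMR or for the repeat angiogram.
- **Comparator.** Sections 4.3, 5, 10.1 and 12.2 all name matched OxAMI patients as the controls. None limits them by culprit vessel.

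**The concern.** There is no randomisation, and study participants who do not receive PICSO have no CMR. Every infarct-size comparison, early and at 6 months, therefore rests on how alike the PICSO and historical groups are. Apart from the common requirement of IMR above 40, the list in 12.2 is the only stated control of confounding, and none of its seven variables identifies the culprit vessel.

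The vessel mixes could differ for a concrete reason. Version 5.0 widened eligibility by location while recruitment was under way, whereas the OxAMI controls come from a general STEMI cohort with no stated vessel limit. If vessel also predicts infarct size without PICSO, a difference in mix would appear as a treatment effect or would hide one. The estimate at stake is the infarct-size effect, which is the Synopsis primary endpoint and the basis of the sample size.

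**Working it through.** **1. The plan's own figure.** Section 12.1 gives 12 per group for a 29% reduction with 95% confidence and 80% power, later raised to 25 per arm. It gives no control mean or SD, so the 12 can be neither confirmed nor refuted. It can only be solved backwards.

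Assume a two-sample t-test at two-sided 5%, with degrees of freedom 2n − 2, noncentrality d·√(n/2) and d = difference/SD.

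- At n = 12 (22 df), 80% power needs d = 1.197 (noncentrality 1.197 × √6 = 2.93).
- Implied SD = 29/1.197 = 24.2% of the control mean.
- At n = 25 (48 df), noncentrality = 1.197 × √12.5 = 4.23, and power = 98.6%.

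The implied SD depends on the test assumed: about 25% with a two-sided normal approximation and 29% with a one-sided one.

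**2. How much bias matters at 25 per arm, with no vessel input.** Let b be the bias as a percentage of the control mean. False benefit is the upper-tail rejection rate with d = b/24.2. Power with a bias against PICSO uses d = (29 − b)/24.2.

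- No bias: false benefit 2.5%, power 98.6%.
- b = 2.2 toward benefit: d = 0.091, noncentrality 0.32, false benefit 5.0%. This is 2.2/29 = 8% of the target effect.
- b = 9.4 against PICSO: d = 19.6/24.2 = 0.809, noncentrality 2.86, power 80%. This is 9.4/29 = 32% of the target effect.

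**3. Illustration with assumed inputs.** The documents give neither input. Assume that untreated infarct size differs between LAD and non-LAD culprits by 20% of the control mean, and that the LAD share differs between groups by 10, 20 or 30 points. Then b = gap × imbalance.

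| LAD imbalance | b (% of control mean) | Power if against PICSO, SD 24.2 | False benefit if toward PICSO, SD 24.2 | Power, SD 36 | False benefit, SD 36 |
|---|---|---|---|---|---|
| 10 points | 0.20 × 10 = 2 | 97.1% | 4.7% | 73.8% | 3.9% |
| 20 points | 0.20 × 20 = 4 | 94.7% | 8.3% | 67.2% | 5.8% |
| 30 points | 0.20 × 30 = 6 | 90.8% | 13.5% | 60.0% | 8.3% |

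The SD of 36% is the value at which 25 per arm gives about 80% power (79.7%) without bias. It shows how the result moves if infarct size is more variable than step 1 implies. A simulation that mixes the two vessel groups explicitly (controls 50% LAD, total SD 24.2) gives power of 97.3%, 94.9% and 91.8%, and false benefit of 4.7%, 8.3% and 14.1%, close to the table.

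**4. Could the groups differ by chance alone?** If both groups had the same underlying LAD share, assumed between 50% and 70%, two unmatched samples of 25 would differ by 20 points or more in 16% to 20% of cases.

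**5. The null case.** If vessel does not predict untreated infarct size, the gap is zero and so is b, whatever the imbalance.

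**The case against.** **The list may not be final.** Section 12.2 says that the model includes these predictors, not that it is limited to them, and it promises expert statistical advice. A reader might infer a closed list that rules vessel out; the wording does not go that far. But a variable that later advice might add is not pre-specified, so the gap remains.

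**The confounding link is not in the documents.** A reader might take Section 4.2 to mean that anterior infarcts are larger without treatment. It speaks only of expected response to the device, which is effect modification. Matching on vessel would not by itself resolve that. Nor do the documents say how many PICSO patients were enrolled before and after version 5.0. This stands, and it limits the point to a possible confounder.

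**Other endpoints help.** Section 5 lists area at risk and myocardial salvage beside infarct size. Salvage partly accounts for territory. The relief is partial, because 12.2 does not adjust infarct size for area at risk.

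**Larger biases can be computed.** A reader might try a 40% vessel gap with a 30-point imbalance, which at SD 24.2 gives 68% power or 40% false benefit. With controls 50% LAD, that gap implies a between-vessel SD of 20, so vessel would explain 400/587 = 68% of all infarct-size variance. The mixture simulation also differs there (74% and 45%). That case is too strained to carry the argument.

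**Stent volume.** It is fixed at Stage 3, after PICSO starts at Stage 2, so a reader might infer that matching on it removes part of the treatment effect. The documents do not show that PICSO changes stent volume, so no bias is demonstrated.

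**Conclusion.** The point holds as a gap in the stated control of confounding that should be fixed, with medium confidence. Culprit vessel is neither matched nor adjusted for in the only infarct-size comparison, although eligibility now covers every location and the protocol itself treats location as relevant to response.

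The documents do not support the stronger conclusion that the comparison is biased. Size and direction are unknown, and the bias may be zero. The thresholds in the working rest on a two-sided t-test and a back-solved SD, and the table also rests on an assumed vessel gap and imbalance. On those assumptions, a moderate imbalance costs little power (97% to 91% at SD 24.2) but can raise false benefit from 2.5% to between 5% and 14%.

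**What to change.** In Section 12.2:

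1. Match exactly on culprit vessel (LAD versus non-LAD). If that leaves too few pairs, add vessel to the propensity score instead.
2. Report the vessel mix of each group before and after matching.
3. Add a vessel-adjusted infarct-size analysis as a sensitivity analysis.

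**Cost.** The change is to analysis wording and needs no new measurement in PICSO patients, because the index angiogram shows the culprit vessel; the same should hold for the OxAMI controls, who also had primary PCI. The real downside is the matching pool. Section 8.1.1.1 puts OxAMI at about 250 emergency PCI participants, but the number with IMR above 40 and complete recath and CMR data is not given. Exact matching divides that pool, and some PICSO patients may lack a close control; adding vessel to the score is the fallback.

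**Optional.** Add a sensitivity analysis without stent volume. Reconcile Section 9.4, which places the pressure wire in the culprit artery in one sentence and in the LAD in another.

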13 DATA MANAGEMENT

13.1 Source Data

Source documents are where data are first recorded, and from which participants' CRF data are obtained. These include, but are not limited to, hospital records (from which medical history and previous and concurrent medication may be summarised into the CRF), clinical and office charts, laboratory and pharmacy records, diaries, microfiches, radiographs, and correspondence.

CRF entries will be considered source data if the CRF is the site of the original recording (e.g. there is no other written or electronic record of data). All documents will be stored safely in confidential conditions. On all trial-specific documents, other than the signed consent, the participant will be referred to by the trial participant number/code, not by name.

13.2 Access to Data

Direct access will be granted to authorised representatives from the Sponsor, host institution and the regulatory authorities to permit trial-related monitoring, audits and inspections.

13.3 Data Recording and Record Keeping

Study data will be entered on case record forms (CRF). The department SOP on database design will be followed. Data will be uploaded into SPSS or equivalent statistical software for statistical analysis. The participants will be identified by a study specific participant number in any database. The name and any other identifying detail will NOT be included in any study data electronic file. All data will be made non patient-identifiable as soon as is practical to do so via the participant ID.

14 QUALITY ASSURANCE PROCEDURES

The trial will be conducted in accordance with the current approved protocol, ICH GCP, relevant regulations and standard operating procedures.

Regular monitoring will be performed by the sponsor according to ICH GCP. Data will be evaluated for compliance with the protocol and accuracy in relation to source documents. Following written standard operating procedures, the monitors will verify that the clinical trial is conducted and data are generated, documented and reported in compliance with the protocol, GCP and the applicable regulatory requirements.

15 SERIOUS BREACHES

A serious breach is defined as “A breach of GCP or the trial protocol which is likely to affect to a significant degree –

- (a) the safety or physical or mental integrity of the subjects of the trial; or
- (b) the scientific value of the trial”.

In the event that a serious breach is suspected the Sponsor must be contacted within 1 working day. In collaboration with the C.I., the serious breach will be reviewed by the Sponsor and, if appropriate, the Sponsor will report it to the REC committee, Regulatory authority and the NHS host organisation within seven calendar days.

16 ETHICAL AND REGULATORY CONSIDERATIONS

16.1 Specific Ethical Considerations for participants in emergency situations

Research in emergency situations is ethically complex because of the urgent nature of the interventions and the often severely compromised capacity of the patient. The processes of enrolment and consent described above, including verbal consent and assent, the involvement of the Advocate represents our attempt to develop a thorough, ethically justified process that both protects patients' rights and interests and enables important research to be done. These processes have been developed in the light of and guided by the provisions laid out in the Mental Capacity Act with special reference to Section 32(9).

16.2 Possible risks and/or discomfort for patient

Patients referred for cardiac catheterization and PCI will undergo this procedure as would routinely be performed. Patients will therefore be consented for the standard of care procedure and its associated risks.

Overall the PCI procedure time may be lengthened by around 20 minutes to complete the selected study procedures (cardiac physiological measurements + PICSO catheter placement). In the context of a PCI procedure that typically last approximately 60 minutes; the additional time taken should not result in any clinically significant difference to the participants. Very occasionally this additional time can result in some back discomfort for patients having to lie on the angiography bed for the additional time period.

CMR is an established cardiac imaging technique in our institution and is generally very well tolerated. Specific considerations for safety are reflected by the additional exclusion criteria listed in section 7.3. All local protocols will be adhered to and only fully trained staff will carry out procedure according to departmental SOPs.

16.3 Collaboration and Partnership with Commercial Companies

The University of Oxford, the Oxford University Hospitals NHS Trust (OUHT) and the OxAMI-PICSO study may work in partnership with, and receive support from, commercial companies who provide the devices

and technologies related to PCI and other research investigations. As part of this partnership we may make available research data to the company specifically related to the use of their device or technology. All data will be supplied in a fully anonymised format and participants would not be identifiable from this.

16.4 Feasibility

16.4.1 Facility

The Oxford Heart Centre is a state-of-the-art facility which incorporated services in cardiology and cardiac surgery. The cardiac catheter laboratories are fully equipped to support these studies.

16.5 Declaration of Helsinki

The Investigator will ensure that this trial is conducted in accordance with the principles of the Declaration of Helsinki.

16.6 ICH Guidelines for Good Clinical Practice

The Investigator will ensure that this trial is conducted in full conformity with relevant regulations and with the ICH Guidelines for Good Clinical Practice (CPMP/ICH/135/95) July 1996.

16.7 Medical Device regulations

The Investigator will ensure that this trial is conducted in full conformity with:

- European Commission Medical Device Guidelines relating to the application of the EU Directives on Medical Devices
- Guide to European Medical Device Trials and BS EN ISO 14155

16.8 Approvals

The protocol, informed consent form, participant information sheet and any proposed advertising material will be submitted to an appropriate Research Ethics Committee (REC), and host institution(s) for written approval.

The Investigator will submit and, where necessary, obtain approval from the above parties for all substantial amendments to the original approved documents.

16.9 Reporting

The CI shall submit once a year throughout the clinical trial, or on request, an Annual Progress Report to the REC, host organisation and Sponsor. In addition, an End of Trial notification and final report will be submitted to the REC, host organisation and Sponsor.

16.10 Participant Confidentiality

The trial staff will ensure that the participants' anonymity is maintained. The participants will be identified only by initials and a participants ID number on the CRF and any electronic database. All documents will be stored securely and only accessible by trial staff and authorised personnel. The trial will comply with the Data Protection Act, which requires data to be anonymised as soon as it is practical to do so.

16.11 Potential Benefits

The information derived from coronary pressure/flow measurements is often very useful to the interventional cardiologist in optimising PCI strategy, and the use of vasodilators (e.g. adenosine) as part of the coronary pressure/flow measurements often results in useful clinical improvements in coronary flow.

Finally PICSO treatment, according to pre-clinical literature evidences, is expected to provide a benefit in terms of infarct size reduction. According to animal models this advantage should amount around a 29% in reduction of the infarcted area. The application of PICSO treatment in a highly selected, high risk population of STEMI patients should amplify the potential benefits of this therapy.

